## BACKGROUND AND CURRENT STATUS OF THE ISSUE

### **Introduction.**

Spain is one of the countries with the highest life expectancy at birth in the world, with a life expectancy of 80.0 years for men and 85.6 years for women in 2015 (1). This has led to a considerable increase in the population of elderly people over the last century (2).

This increase does not imply that this high life expectancy is accompanied by years of good health, as older people may suffer from diseases and health problems that lead to a loss of quality of life, without resulting in immediate death (3-5).

One of the most important problems associated with ageing is hip fractures, as it generates a significant impact in terms of morbidity, mortality and functional deterioration. In Spain, this problem causes an incidence of 103 cases per 100,000 inhabitants, with the rate increasing from the age of 75 onwards to 2,534 per 100,000 inhabitants (6.7).

Hip fractures have a very important impact on older people, since in addition to their functional impact on gait, they have an associated inability to perform other activities of daily living and a cognitive impact (8).

Following hip fractures, these patients require many modifications to their daily lives, ranging from increased assistance at home to the need for residential care. This leads to increased health care costs, not only during the hospital stay, but also after discharge (9).

Different clinical practice guidelines have been published in recent years with recommendations aimed at reaching a consensus and improving the care of patients with this pathology (10-13). Despite these recommendations, their implementation in Spanish hospitals has been irregular, generating great variability in the care provided in this process. This has led to differences in patient care depending on the hospital where the patient has been treated, such as: delays in the performance of surgeries, an increase in the number of days of hospitalisation, differences in the number of rehabilitation sessions and differences in the number of consultations (14,15).

What does seem clear is that every elderly person who suffers a hip fracture should undergo a comprehensive assessment including: the cause of the fall, assessment of comorbidity and clinical stability, previous medications, pain, nutritional and hydration status, continence, and cognitive, functional and social status (11).

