### Specific objectives

- To describe the improvement in gait ability in patients undergoing hip surgery after a functional recovery programme compared to the historical control group (exposed cohort).
- To describe the clinical and functional characteristics of the patients operated on for hip fracture in the SJD hospital in León who are being followed up by the new system of care implemented in comparison with the historical control group (exposed cohort).
- To analyse risk and protective factors related to the level of dependency and mortality at 30 days and one year of follow-up in patients operated on for hip fracture at the SJD hospital in León.
- To describe the impact of a functional recovery programme on the prevention and treatment of sarcopenia in the new unexposed cohort.
- To describe the quality of life and patient-reported outcomes in the new unexposed cohort.
- To analyse the impact of a functional recovery programme on the prevention of falls in elderly patients who have undergone hip fracture surgery.

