#### **Variables**

In the two groups that form part of this study, different variables specified in the database adapted from the National Hip Registry and the *International Fragility Fracture Network*, of which the HSJD is a member, will be collected.

Until now, data collection and patient follow-up was completed after one month and the data was transferred annually to the National Hip Fracture Register. In the new model proposed by orthogeriatrics unit of the HSJD, patients will be followed up in person at one and a half months, four months and one year, and at discharge, one month after discharge, three months, six months and one year, by means of a digital application.

The variables to be collected are described below:

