#### **First group: variables established in the National Hip Fracture Registry, defined according to its protocol**

These scales will be administered to both groups:

- Cohort of unexposed patients: to be administered on the dates indicated.

- Cohort of exposed patients (retrospective): data will be retrieved from the Exceldata collection system that the medical management of the HSJD manages for the follow-up of these patients and the report to the national hip fracture registry.

These variables include socio-demographic, clinical and functional characteristics prior to surgery (Table I):

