**Table I: Sociodemographic, clinical and functional characteristics prior to surgery.**

Variables	Unit of measurement	Type
Age	Years	Independent quantitative
Genre	H- Male M- Female	Independent qualitative
Caregiver	1- Yes 2- No 3- Live alone	Independent qualitative
Preoperative mental assessment. Pfeiffer Test (SPMSQ-VE)	Points (0 to 10)	Qualitative
Mobility RNFC ladder	Levels (1 to 11)	Qualitative
Pre-fracture mobility. Gait assessment scale (mFAC).	Levels (0 to 6)	Qualitative
Side affected by the fracture	D- Law I- Left	Qualitative
Abbreviations: SPMSQ-VE: Short Portable Mental Status Questionnaire, (mFAC): Modified Functional Ambulatory Classificator, RNFC: Registro Nacional de Fractura de Cadera.		

- **Preoperative mental assessment. PfeifferTestor "Short Portable MentalStatusQuestionnaire" (SPMSQ-VE) (32)**

It assesses the patient's cognitive status at the time of administration. It consists of 10 questions that are asked prior to surgery, inwhich errors are computed. The test should be performed as close to the patient's baseline cognitive state as possible.

The inter- and intra-observer reliability of the SPMSQ-VE is 0.738 and 0.925 respectively, with an internal consistency value of 0.82 (32)

Pfeiffer test translated and validated in Spanish

1. What day is today? (Month, day, year).
2. What day of the week is today?
3. Where are we now?
4. What is your telephone number? (If no telephone, street address).
5. How old are you?
6. What is your date of birth?
7. Who is the current Prime Minister?
8. Who was the previous Prime Minister?
9. Tell me your mother's first surname.
10. Starting at 20, subtract 3 by 3 successively until you reach 0.

Errors are scored, 1 point per error. A score of three or more indicates cognitive impairment. If the educational level is low (elementary education), one more error is allowed for each category. If the level of education is high (university), one level less is allowed.

This scale is only administered prior to surgery to assess the patient's cognitive status.

This scale is administered on entry.

- **Pre-fracture mobility, according to the national fragility hip fracture registry(33).**

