### **Limitations of the study**

The project poses a number of constraints that need to be taken into consideration:

- The current pandemic situation affecting the hip fracture care process.

- The necessary involvement of the relative or the residence in the therapeutic process.
- Adherence to the application for data collection from the patient's experience.
- The use of a mobile application for data collection and the implementation of the recovery programme in an ageing population. A specific follow-up will be established by the research team to support participants who present any kind of difficulty.
- Thosederived from an observational study, which is not conducted under the control and randomisation conditions of a clinical trial

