**Description of the process:**

- Candidate selection: the patient will be cared for by orthogeriatrics unit according to its standard clinical practice protocol approved by the medical management, and based on the care model established by the National Hip Fracture Registry.
- If the patient is admitted from the emergency department, a referral to geriatrics will be requested to assess the patient.
- Explanation of the programme and request for informed consent (Annexes VI and VII): at the time of admission, an interview will be held between the patient or relative and the doctor in charge (traumatology service) explaining the process for patients with osteoporotic hip fracture in the Hospital; which encompasses the set of coordinated medical decisions (Emergency, Traumatology, Geriatrics) with the aim of obtaining the highest quality care, shorter hospital stay with the maximum level of independence and avoiding a second fracture. In the same way and at the same time, the multimodal plan of therapeutic exercise and functional recovery that will help them during their recovery process will be explained to them.

Subsequently, the patient will be informed of the data collection process, mobile application and follow-up for 1 year, and signatures will be requested for informed consent for anaesthesia, surgery and participation in the study. If the patient accepts, Caaring® application.

Profiles of patients whose clinical circumstances permit, a corroborated history should be taken, including:

- Premorbid function and mobility.
- Available social support (including whether the patient already has a caregiver or whether someone is willing and able to provide such support)
- Relevant current clinical conditions
- State of mind.
- Hip Surgery.
- Recovery programme (protocol of action that replaces the usual practice developed previously):
  - Specific hip fracture recovery programme, restoring the mobility, strength and balance of the operated patient, in order to facilitate the return to a functional state as close as possible to the state prior to surgery and in the shortest possible time, as detailed in Annex VIII. This programme is part of the standard treatment protocol implemented since January 2021 by the Orthogeriatrics Unit of the HSJD.

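### Tables I–III name no baseline comorbidity, time to surgery, fracture type, operation or prior residence, so no listed variable covers them in the 2020–2021 comparison or the risk-factor analysis

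*Combined protocol and SAP*

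**What the plan says.** The Variables section says that both groups contribute "different variables specified in the database adapted from the National Hip Registry" and from an international fracture network, and then that "The variables to be collected are described below". The first group of variables, for both cohorts, is introduced with "These variables include socio-demographic, clinical and functional characteristics prior to surgery (Table I". Table I has seven rows: age, sex, caregiver (yes, no, lives alone), Pfeiffer test, RNFC mobility, mFAC, and "Side affected by the fracture". Table II, which the protocol says can be measured only in the 2021 cohort, holds follow-up scales and a list of postoperative events. Table III is the timetable for those scales.

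One specific objective is "To analyse risk and protective factors related to the level of dependency and mortality at 30 days and one year of follow-up". The Introduction puts comorbidity and clinical stability within the assessment every such patient should have. It treats prompt surgery as desirable and apparently important for regaining function. It also names "delays in the performance of surgeries, an increase in the number of days of hospitalisation" among the ways care differs between hospitals. The first constraint under Limitations of the study is "The current pandemic situation affecting the hip fracture care process". For 2021 admissions, Description of the process asks for a history that covers "Relevant current clinical conditions".

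**The concern.** The main comparison sets one calendar year against the next without randomisation, and the protocol itself says the pandemic affected the care process. The cohorts also differ by design. Under the eligibility criteria, only 2021 patients need smartphone access and signed consent, only they can be excluded for unaccompanied cognitive impairment, and only they can be withdrawn for complications or non-compliance. Differences in case mix are therefore plausible.

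If comorbidity and surgical delay are not in the dataset, a difference between the years in either could be read as an effect of the programme, or could hide one. In the risk-factor analysis, an association that belongs to an unrecorded factor may be credited to a listed one, such as age or mobility, wherever the two are correlated.

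**Working it through.** The plan gives no figure on this point to reproduce. Its only sample figure, 67, is offered as grounds for assuming normality and does not enter here. The check is of content, followed by an illustration.

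**1. Each factor looked for in Tables I, II and III**

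| Factor | Listed? | Nearest listed item | What the text says about it |
|---|---|---|---|
| Baseline comorbidity | No | Postoperative events (Table II, 2021 only) | Part of the assessment every patient should have (Introduction) |
| Time to surgery | No | None | Early operation desirable and apparently important for function; delay varies between hospitals (Introduction) |
| Fracture type | No | Side, left or right | Not presented as prognostic |
| Operation | No | None | Not presented as prognostic |
| Residence before admission | No | Caregiver item, with a living-alone category | Residential care is a consequence of fracture (Introduction); the residence's involvement is a constraint (Limitations) |
| Length of stay | No | None | Varies between hospitals (Introduction); a shorter stay is an aim of care (Description of the process) |

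Result: 0 of 6 are listed, with a partial trace of residence in the caregiver item.

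**2. Is the list closed?** Two statements leave it open: the variables come from a registry-adapted database, and the first group is said to include Table I. Three point the other way. The list is announced as what will be collected. The confidentiality paragraph under Ethical aspects limits collection to data the study needs. The text after Table III describes the study variables as part of a wider clinical record and says that those established for this study will be extracted. An unlisted field may therefore exist, but it has no stated route into the analysis dataset.

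**3. The admission history.** Of the items in that history, prior mobility and social support have counterparts in Table I (RNFC, mFAC, caregiver). Current clinical conditions have none.

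**4. Use in analysis.** The analysis paragraph of the work plan gives t-tests and chi-square tests for baseline characteristics. It names no adjusted model and no risk-factor model, so even the seven listed items have no stated role in adjustment.

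**5. Which factors could be adjusted for?** Description of the process starts the programme the day after the fracture. Comorbidity, fracture type and prior residence are settled before that. Time to surgery and operation are settled after admission and may form part of how care changed between years. Length of stay follows the start of the programme and could be altered by it.

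**6. Illustration of size.** For one unrecorded yes/no factor and no true programme effect:

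spurious difference in recovery = (difference in its prevalence between years) × (its effect on recovery)

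Both inputs are assumptions, with prevalence gaps of 5 to 20 points and effects of 10 to 30 points:

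- 0.05 × 0.10 = 0.005, or 0.5 points
- 0.10 × 0.20 = 0.02, or 2 points
- 0.20 × 0.30 = 0.06, or 6 points

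A larger gap of 30 points with an effect of 25 points gives 0.30 × 0.25 = 0.075, or 7.5 points. These are crude values. They can go in either direction, and adjustment for age, cognition and prior mobility would absorb an unknown part.

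**The case against.** The strongest reply is that the list may not be complete. The variables are drawn from a registry-adapted database, the 2020 data come from the hospital's registry submission, and Table I is introduced in non-exhaustive terms. The missing fields may already sit in that file. This stands as far as it goes: a reader might infer that the data are absent and that no model could ever adjust for them, and the documents do not show that. They also do not show that the fields exist or will be used, and the extraction wording favours the listed set.

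A reader might also infer that the protocol treats all these factors as decisive. It does not. Its own text supports comorbidity and time to surgery. Hospital days and surgical delay are mentioned as variation between hospitals, and this is a single-hospital study. Residential care appears as a consequence of fracture. The case for fracture type, operation and prior residence rests on ordinary case-mix reasoning.

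Three further points are fair. Cognition and pre-fracture mobility are recorded and cover part of the case mix. The Limitations section already discloses the pandemic and the lack of randomisation, although disclosure does not supply a covariate. Added fields would also change nothing without a stated model, which is why the remedy must include their use.

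**Conclusion.** The concern holds in a limited form. No listed variable measures baseline comorbidity, time to surgery, fracture type, operation or residence before admission. As written, the plan therefore gives a non-randomised comparison across two pandemic years, and a risk-factor analysis of dependency and mortality, without a listed measure of the two factors its own Introduction stresses. This is a change that should be made, not a fatal flaw.

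The conclusion rests on reading the tables together with the extraction wording. If the database does hold these fields and they will be used, the remedy reduces to naming them. The size of the confounding cannot be derived from the documents, and the 0.5 to 6 points above illustrates assumed inputs only. It would also go too far to say that the risk-factor analysis will certainly misattribute effects, because that needs a correlation between omitted and listed factors for which the documents give no evidence. Nor does it follow that every missing item is a confounder: adjusting for length of stay could remove part of the programme's effect or introduce bias.

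**What to change.** Amend Table I to name, for both cohorts:

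- dates of admission and surgery, giving time to surgery
- fracture type and operation type
- one routine comorbidity or anaesthetic-risk grade
- residence before admission
- date of discharge, for description only

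Take them from the register file or the hospital record, and report their balance between 2020 and 2021. Then state how they will be used:

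- **Between-cohort comparison, main analysis:** adjust for comorbidity or risk grade, fracture type and residence, with age, sex, Pfeiffer score and pre-fracture mobility.
- **Between-cohort comparison, sensitivity analysis:** add time to surgery and operation type.
- **Risk-factor analysis:** use the main adjustment set plus time to surgery and operation type.
- **Length of stay:** report it descriptively or as an outcome, and do not adjust for it.

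Fix the model terms in advance and keep them few, since the plan does not say whether 67 is a total or a per-group number. If a field is missing for 2020, say so and limit the conclusion accordingly.

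The cost is some extraction time, a protocol amendment and possibly incomplete 2020 fields. That the hospital's records hold these fields is likely but is not stated in the documents.

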#### **First group: variables established in the National Hip Fracture Registry, defined according to its protocol**

These scales will be administered to both groups:

- Cohort of unexposed patients: to be administered on the dates indicated.

- Cohort of exposed patients (retrospective): data will be retrieved from the Exceldata collection system that the medical management of the HSJD manages for the follow-up of these patients and the report to the national hip fracture registry.

These variables include socio-demographic, clinical and functional characteristics prior to surgery (Table I):

**Table I: Sociodemographic, clinical and functional characteristics prior to surgery.**

Variables	Unit of measurement	Type
Age	Years	Independent quantitative
Genre	H- Male M- Female	Independent qualitative
Caregiver	1- Yes 2- No 3- Live alone	Independent qualitative
Preoperative mental assessment. Pfeiffer Test (SPMSQ-VE)	Points (0 to 10)	Qualitative
Mobility RNFC ladder	Levels (1 to 11)	Qualitative
Pre-fracture mobility. Gait assessment scale (mFAC).	Levels (0 to 6)	Qualitative
Side affected by the fracture	D- Law I- Left	Qualitative
Abbreviations: SPMSQ-VE: Short Portable Mental Status Questionnaire, (mFAC): Modified Functional Ambulatory Classificator, RNFC: Registro Nacional de Fractura de Cadera.		

- **Preoperative mental assessment. PfeifferTestor "Short Portable MentalStatusQuestionnaire" (SPMSQ-VE) (32)**

It assesses the patient's cognitive status at the time of administration. It consists of 10 questions that are asked prior to surgery, inwhich errors are computed. The test should be performed as close to the patient's baseline cognitive state as possible.

The inter- and intra-observer reliability of the SPMSQ-VE is 0.738 and 0.925 respectively, with an internal consistency value of 0.82 (32)

Pfeiffer test translated and validated in Spanish

1. What day is today? (Month, day, year).
2. What day of the week is today?
3. Where are we now?
4. What is your telephone number? (If no telephone, street address).
5. How old are you?
6. What is your date of birth?
7. Who is the current Prime Minister?
8. Who was the previous Prime Minister?
9. Tell me your mother's first surname.
10. Starting at 20, subtract 3 by 3 successively until you reach 0.

Errors are scored, 1 point per error. A score of three or more indicates cognitive impairment. If the educational level is low (elementary education), one more error is allowed for each category. If the level of education is high (university), one level less is allowed.

This scale is only administered prior to surgery to assess the patient's cognitive status.

This scale is administered on entry.

- **Pre-fracture mobility, according to the national fragility hip fracture registry(33).**

Gait is the parameter most strongly associated with frailty states, with gait speed being the parameter most commonly associated with frailty(34,36). This is why it is so important to recover functions and capacities in this area of movement. This scale is very easy to use and apply and is used by the national fracture registry, which allows us to make comparisons and statistical analyses with the results published with this registry.

It assesses by ability levels ranging from 0 to 11. Its design allows firstly to determine gait ability and secondly to see the evolution and establish treatment guidelines.

Capacity levels:

- Level 1-Independent mobility inside and outside the home without technical aids
- Level 2- Independent mobility inside and outside the home, with technical assistance.
- Level 3- Independent mobility inside and outside the home with two technical aids or walker.
- Level 4- Independent mobility only indoors without technical assistance.
- Level 5- Independent mobility only indoors with a technical aid.
- Level 6- Independent mobility only indoors with two technical aids or walker.
- Level 7- Independent mobility only within the house under personal supervision.
- Level 8- Mobility only within the home with little assistance from a person.
- Level 9- Mobility only within the home with a lot of help from a person.
- Level 10- Mobility with two people or no mobility.
- Level 11- Unknown.

For simplicity this variable is summarised in these questions:

- Technical aids (yes/no).
- Outside/inside the home.
- And note the best situation, i.e. it is better with a cane outside than without help at home.

This scale is administered at admission, 6 weeks, 4 months and 1 year.

• ***ModifiedFunctionalAmbulatoryClassifier(mFAC)(36).***

It is a scale that assesses different levels of ability by grading them between 0 and 6. Its design allows firstly to determine gait ability and secondly to see the evolution and establish treatment guidelines. The modified gait assessment scale has shown an intraclass correlation coefficient(ICC)= 0.960, with a 95% confidence interval: 0.942-0.972, an inter-observer agreement Cohen's kappa index of 0.83 (CI: 0.69-0.97) and a validity p= 0.814 (36-38)

The capacity levels for this scale are:

- Level 0: Patient who cannot remain seated for more than 1 minute without the help of the backrest and armrest.
- Level 1: Patient who can remain seated without the aid of the backrest and armrest for more than 1 minute.
- Level 2: non-functional ambulation. Walking with great physical assistance from a person, and/or walking is only possible within a therapy session at home, or in hospital, between parallel bars
- Level 3: ambulation in the home, walking with light physical contact with a person. Is able to walk only indoors, on flat, horizontal surfaces, usually within a defined area.
- Level 4: walks autonomously in the home or neighbourhood environment, but needs supervision by a person. They can walk on uneven surfaces and can climb an occasional step.
- Level 5: independent community walking. Can walk on uneven terrain, up and down steps, ramps, kerbs, etc. Can walk considerable distances, but with obvious limp.
- Level 6: walks normally both indoors and outdoors, in the absence of a limp or other abnormality.

This scale is administered at admission, 6 weeks, 4 months and 1 year.

**Second group: the variables collected in this second section form part of the new model of care established by the orthogeriatric service, whereby the hip fracture patient will be followed up for up to one year after the intervention, therefore, they are variables that can only be measured in the cohort of unexposed patients.**

Patient follow-up variables (Table II):

